#### 2.4.3. Overall Benefit: Risk Conclusion

This is the first time that ALXN1910 will be administered to humans. Healthy participants are the appropriate population for this study as they will enable PK and PD assessments without the potential of confounding effects due to other disease activity, comorbidities, or concomitant medications.

ALXN1910 is a next-generation ERT of asfotase alfa. In 2015, a healthy participant study has been completed for asfotase alfa (Study AA-HV-104), which tested a single 2 mg/kg dose by SC injection. Asfotase alfa was generally well tolerated with an acceptable safety profile. No NAb response to asfotase alfa was observed in any of the treated healthy participants at 42 days post dose, suggesting a very low risk to healthy participants with short term dosing of asfotase alfa. As the catalytic domains of ALXN1910 and asfotase alfa are structurally 99.8% identical, it is anticipated that ALXN1910 and asfotase alfa will possess pharmacologic and immunological similarities and share the same safety profile. Additional results for this study are provided in the ALXN1910 IB.

This study has been designed to minimize the identified potential risks to participants; there are strict inclusion/exclusion criteria with a robust safety monitoring and risk mitigation plan in place.

As described in Section 4.1, a sentinel group will be implemented for each cohort. The first 2 participants randomized to each cohort will be dosed as a sentinel pair with 1 participant on active treatment and 1 participant on placebo. This dosing strategy is justified given the large safety margin (approximately 15-fold [based on predicted AUC0-168h value] at the highest

planned single dose of 135 mg SC). A sentinel safety report will be produced and reviewed before dosing the remaining participants in each cohort.

At the discretion of the Investigator, up to 3 more participants will be dosed at least 48 hours after dosing of the sentinel pair, followed by dosing of the remaining participants in the cohort no earlier than 72 hours after sentinel pair dosing, as long as no suspension/stopping criteria have been met. At no time will more than 4 participants per cohort be dosed in a given day.

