#### 4. STUDY DESIGN

# 4.1. Overall Design

This is a Phase 1, randomized, double-blind, placebo-controlled study designed to evaluate the safety, tolerability, PK, PD, and immunogenicity of SADs of ALXN1910 SC and a SAD of ALXN1910 IV in up to approximately 48 healthy adult participants across treatment cohorts (up to approximately 36 participants to receive ALXN1910 and up to approximately 12 participants to receive placebo) (Table 5).

Of the 48 participants, 8 will be of Japanese descent, defined as those participants whose parents and grandparents are both Japanese and who have spent less than 10 years outside of Japan. The inclusion of Japanese participants aims to meet the regulatory requirements of the ICH Guidance E5(R1), which provides a general framework for evaluating the potential impact of ethnic factors on the acceptability of foreign clinical data.

For this FIH study, 8 participants will be randomly assigned in a 3:1 ratio to treatment and placebo in each of the 6 cohorts with escalating doses of 5 mg IV (Cohort 1), 15 mg SC (Cohort 2), 15 mg IV (Cohort 3) in parallel with 15 mg SC in Japanese participants (Cohort 4) and 45 mg SC (Cohort 5), followed by 135 mg SC (Cohort 6). The first 2 participants randomized to each cohort will be dosed as a sentinel pair, with 1 participant on active treatment and 1 participant on placebo. This dosing strategy is justified given the large exposure margins (approximately 15-fold at the highest planned single dose of 135 mg SC).

At the discretion of the Investigator, up to 3 more participants will be dosed at least 48 hours (as anticipated tmax occurs prior to 48 hours postdose) after the dosing of the sentinel pair, followed by dosing of the remaining participants in the cohort no earlier than 72 hours after sentinel pair dosing, as long as no suspension/stopping criteria have been met. At no time will more than 4 participants per cohort be dosed in a given day.

Participants who meet the qualifications for the study based on screening will be admitted to the CRU the day prior to dosing (Day -1) to undergo Check-in assessments per the applicable SoA (Section 1.3).

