## 6.6. Dose Modification

Decisions to continue or modify dosing will be made by the Investigator and/or SRC after review of the blinded data as described in Table 8. The SRC may also make recommendations regarding safety issues, study conduct, or study suspension.

Predicted ALXN1910 human PK exposure (Table 6) indicates Cohort 5 or Cohort 6 mean projected PK exposure should not exceed 50% of the NOAEL exposure established in the 28-day GLP toxicology study in monkeys. In the event that mean PK exposure in Cohort 5 or Cohort 6 is predicted to exceed 50% of the NOAEL exposure, a lower dose will be selected so the above criteria can be met. PK data will not be used for dose escalation from Cohort 1 to Cohort 2 as greater than 150-fold PK (safety) exposure margin is expected for Cohort 2.

Dose escalation requires agreement between the Investigator and Alexion; Alexion may not supersede the Investigator if there are concerns that dosing should be stopped.

**Table 8:** Detailed Dose Escalation Criteria for Each Cohort

Dosing Decision	Responsible Party	Data to be Reviewed	Documentation/ Communication Methods
Dose escalation from Cohort 1 to Cohort 2	SRC	• At minimum, 14 days of postdose safety and tolerability data from at least 7 participants in Cohort 1.	The SRC will document the decision on the escalation/progression approval form.
Dose escalation from Cohort 2 to Cohort 5 (in parallel with Cohort 3 and Cohort 4)	SRC	
 
At minimum, 14 days of postdose safety and tolerability data from at least 7 participants in Cohort 2.
 
Seven days of PK data from at least 7 participants in Cohort 1 and at least 7 participants in Cohort 2.
 
	The SRC will document the decision on the escalation/progression approval form.
Dose escalation from Cohort 5 to Cohort 6	SRC	
 
At minimum, 14 days of postdose safety and tolerability data from at least 7 participants in Cohort 5.
 
Seven days of PK data from at least 7 participants in Cohort 5.
 
The cumulative PK data from Cohort 1 and Cohort 2.
 
	The SRC will document the decision on the escalation/progression approval form.

Abbreviations: PK = pharmacokinetic; SRC = Safety Review Committee

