## 7.2. Cohort Stopping Rules

In the event an acute safety event occurs in any cohort, dosing should be stopped until a causality assessment has taken place and an appropriate risk mitigation strategy is put into place before dosing the remainder of the cohort.

Assessment of AE intensity/severity should be performed by the Investigator using clinical judgment and according to criteria from NCI CTCAE version 5.0, published 27 Nov 2017 (see Section 10.3.3). As CTCAE grading is intended for oncology patients, study-specific modifications related to the liver, hematology, and QT interval prolongation have been made to ensure clear guidance and appropriate grading of AEs for this study in healthy participants (Table 11).

If a cohort stopping rule (Table 11) is met, no further dosing at the dose level or higher will proceed. Continuation of the cohort and/or study will require a substantial protocol amendment.

Unless a cohort stopping rule is met, dose continuation or escalation will proceed as scheduled and the study will continue as planned provided no prespecified toxicity events occur (as determined by the SRC).

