## 10.3.4. Reporting of SAEs

#### SAE Reporting to Alexion or Delegate via Paper Safety Reporting Form

- All SAEs will be recorded and reported to Alexion or designee immediately and within 24 hours awareness.
- SAEs will be reported using the Safety Reporting Form and submitted to Alexion GDS. The Investigator
  must complete, sign, and date the SAE pages, verify the accuracy of the information recorded on the SAE
  pages with the corresponding source documents, and send a copy via email or facsimile to the contact
  information provided below:
  - Email: [contact] or Fax: [name]
- Additional follow-up information, if required or available, should be entered into the eCRF and sent to
  Alexion GDS within 24 hours of the Investigator or study site staff becoming aware of this additional
  information via the reporting process outlined above.
- For all SAEs, the Investigator must provide the following:
  - Appropriate and requested follow-up information in the time frame detailed above
  - Causality of the SAE(s)
  - Treatment of/intervention for the SAE(s)
  - Outcome of the SAE(s)
  - Medical records and laboratory/diagnostic information
- All paper forms and follow-up information submitted to Alexion GDS **must** be accompanied by a cover page signed by the Investigator.
- Paper source documents and/or reports should be kept in the appropriate section of the study file.

Abbreviations: AE = adverse event; ALT = alanine aminotransferase; AST = aspartate aminotransferase; eCRF = electronic case report form; CTCAE = Common Terminology Criteria for Adverse Events; ECG = electrocardiogram; GDS = Global Drug Safety; Hb = hemoglobin; SAE = serious adverse event; ULN = upper limit of normal.

**Table 11:** Cohort and Study Stopping Rules

Adverse Events Related to Study Intervention	Showing Signs of Reversibility	Number of Participants	Action
	 	-	~ 1 ~ 5 !
Moderate (CTCAE Grade 2)	Yes	$\geq 3$ in 1 SOC	Cohort: Dosing of the
		$\geq$ 4 total in	remainder of the
	NT.	different SOCs	cohort suspended
	No	$\geq 2$ total in	Study: Dosing of
T ' ' ' ' ' C ' ' ' ' ' ' '	NI o	different SOCs	equal or higher doses
Injection/infusion site reactions:	Noa	≥ 3	suspended
Moderate (CTCAE Grade 2)			Dosing of lower dose
			levels can continue
Injection/infersion related recetions (including	Noa	≥ 3	Continuation of
Injection/infusion related reactions (including hypersensitivity):	No	≥ 3	dosing of equal or
Moderate (CTCAE Grade 2)			higher doses requires

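### Read literally, Table 11 gives related, non-reversible Grade 2 events clustered in one SOC no counted stopping trigger; one cell needs rewording

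*Protocol*

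**What the plan says.** Protocol Section 10.3.4, Table 11, lists the cohort and study stopping rules for adverse events related to study intervention. The general Grade 2 row is split by whether events show signs of reversibility.

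- **Reversible:** "Moderate (CTCAE Grade 2) Yes $\geq 3$ in 1 SOC", and as a second condition at least 4 participants in total across different SOCs.
- **Not reversible:** "No $\geq 2$ total in Study: Dosing of", then "different SOCs equal or higher doses". These lines run across columns. The first gives the reversibility answer, the count and the start of the action; the second completes the count and continues the action. The condition is therefore at least 2 participants in total in different SOCs, and no one-SOC condition is printed.

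Separate Grade 2 rows cover injection/infusion site reactions (at least 3), injection/infusion related reactions including hypersensitivity (at least 3), QT above 500 msec (at least 2) and hemoglobin or platelet drops (at least 2). Grade 3, serious and Hy's law events have their own rules.

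Section 7.2 says that meeting a rule ends dosing at that level and above until a substantial amendment. It also gives the default: "Unless a cohort stopping rule is met, dose continuation or escalation will proceed as scheduled", on the proviso that the Safety Review Committee (SRC) finds no prespecified toxicity event. SAP Section 4.13.9 repeats the SRC text and does not restate the counts.

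**The concern.** The reversible part of the row treats clustering in one SOC and spread over different SOCs as two conditions with two thresholds. Applying the same vocabulary to the non-reversible part means that its single condition covers spread events only. A cluster of non-resolving Grade 2 events in one organ class then has no number attached to it.

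That reverses the order one would want in a first-in-human study in healthy volunteers. Several participants with the same kind of non-resolving event is a stronger signal than the same number with resolving events, yet only the resolving pattern would halt dosing by rule. For the non-resolving pattern, a halt would rest on judgment.

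**Working it through.** **1. The plan's own figure.** The only probabilities stated (Protocol 9.2, SAP 3.2) are for at least one AE among the 6 active participants in a cohort. 1 − (1 − p)^6 at p = 10, 15, 20, 25, 30, 35 and 40% gives 46.9, 62.3, 73.8, 82.2, 88.2, 92.5 and 95.3%, as printed. The documents give no such figures for Table 11.

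**2. The rule applied literally.** Take k affected participants in one cohort, k = 1 to 8, with related Grade 2 events outside the named rows.

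| Pattern | Smallest k that triggers |
|---|---|
| Reversible, one SOC | 3 |
| Reversible, different SOCs | 4 |
| Non-reversible, different SOCs | 2 |
| Non-reversible, one SOC | none, at any k up to 8 |

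If the cell means 2 in total whatever the SOC, the last entry becomes 2.

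**3. Whether another row fills the gap.** The named Grade 2 rows do not. Liver values, for example, appear only in the Grade 3 group: ALT or AST above 3 × ULN with bilirubin above 2 × ULN, above 8 × ULN, or above 3 × ULN with symptoms. Persistent, asymptomatic rises that meet none of these, if graded 2 and judged related, fall to the general row and could all code to one SOC.

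**4. What the missing count would have controlled.** Section 4.1 doses a sentinel pair, then up to 3 more from 48 hours, then the rest from 72 hours. With a second group of 3, 2 + 3 = 5 participants are dosed and 8 − 5 = 3 remain. Those 3 are the within-cohort dosing that a trigger could still prevent. Cohorts 3 and 4 (15 mg) and Cohort 5 (45 mg) may also run in parallel. A trigger at 15 mg would suspend equal and higher doses, including 45 mg; without a trigger, that automatic link is inactive.

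**5. How often a count of 2 would be reached (illustration only).** The per-participant risk p of a related, non-reversible Grade 2 event in one given SOC is my assumption, with participants independent. For the 6 active participants, P(X ≥ 2) = 1 − (1 − p)^6 − 6p(1 − p)^5. At p = 10% this is 1 − 0.5314 − 0.3543 = 0.114.

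| Assumed p | P(X ≥ 2), n = 6 | P(X ≥ 3), n = 6 | P(X ≥ 2), n = 8 |
|---|---|---|---|
| 5% | 3.3% | 0.2% | 5.7% |
| 10% | 11.4% | 1.6% | 18.7% |
| 20% | 34.5% | 9.9% | 49.7% |
| 30% | 58.0% | 25.6% | 74.5% |

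The n = 8 column is an upper bound. It lets placebo participants count at the same risk, since the Investigator judges relatedness blinded. Under the literal text, the chance that this pattern triggers the rule is 0 at every p.

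**The case against.** **Layout.** Table 11 is partly broken in the text copy of the protocol, and broken tables are not errors in the plan. This lowers certainty. The count cells nevertheless read in unbroken sequence, so a lost one-SOC line is unlikely, though not excluded.

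**Intent.** The authors probably meant 2 in total, even if the events fall in different SOCs. On that reading there is no gap, and nothing shows that any site reads it otherwise. This stands, and it makes the point one of wording. But whether a mandatory halt applies should not depend on inferring intent.

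**Other safeguards.** A reader might infer that dosing and escalation would run unchecked past such a cluster. The documents do not support that.

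- Each escalation step (Cohort 1 to 2, 2 to 5, 5 to 6) needs an SRC decision on at least 14 days of safety data from at least 7 participants, documented on an approval form (Table 8).
- Escalation also needs agreement between the Investigator and the sponsor, and "Alexion may not supersede the Investigator if there are concerns that dosing should be stopped" (Section 6.6).
- Within a cohort, Section 4.1 leaves the next group to judgment: "At the discretion of the Investigator, up to 3 more participants will be dosed at least 48 hours".
- Section 2.4.3 adds: "A sentinel safety report will be produced and reviewed before dosing the remaining participants in each cohort". The sentinel pair has only one active participant, so that report alone cannot show a cluster on active drug.
- Section 7.2 adds a pause: "In the event an acute safety event occurs in any cohort, dosing should be stopped until a causality assessment has taken place". No count, grade or SOC defines such an event.
- Section 9.6 allows ad hoc unblinded SRC meetings.

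These safeguards largely remove escalation from the concern. They do not supply the missing count for dosing within a cohort or across parallel cohorts.

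**Threshold.** The table uses 3 for its non-reversible Grade 2 reaction rows, so 2 is not forced for a cluster, and a bare rewording would conflict with those rows. The second half is right and needs a carve-out. On the first, 2 is the general row's own number, and in the reversible part the clustered threshold (3) is below the scattered one (4).

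**Conclusion.** The concern holds as a wording defect in one cell. Read literally, related, non-reversible Grade 2 events confined to one SOC outside the named rows have no counted trigger, while 3 reversible events in one SOC suspend dosing. As probably intended, the threshold is 2. The practical exposure is mainly the remaining participants of a cohort and cohorts running in parallel.

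Two stronger conclusions are not supported. The documents do not show that the sponsor chose a more lenient rule for non-resolving events; the likelier explanation is loose phrasing. Nor do the probabilities above estimate missed stops or harm. They rest on assumed risks, because the documents give no incidence, and they show only how often a count of 2 would be reached.

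The cell should be corrected. Confidence is medium, because it depends on the page image matching the text copy.

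**What to change.** First check the cell against the page image. If it reads as above, reword it to: at least 2 participants in total, in the same or different SOCs, excluding event types that have their own Grade 2 row (injection/infusion site reactions, injection/infusion related reactions, QT prolongation, hematology). Without the exclusion, 2 non-reversible Grade 2 site reactions would trip the general row, although their own row requires 3 and footnote a allows extended observation.

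One side effect needs a decision. If a site reaction plus an event in another SOC now counts toward the total of 2, the exclusion would stop that. If the sponsor wants to keep it, the exclusion can be limited to same-SOC counts.

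A threshold of 3 in one SOC would match the reversible rule, but would make a non-resolving cluster harder to trigger than scattered events.

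The edit is one cell. If sites already read it as 2 in total, the same-SOC wording adds no stops. If they read it literally, dosing may be suspended somewhat more often, each time needing a substantial amendment to resume. Because the last group may be dosed about 24 hours after the second (72 − 48), some events may be counted as non-reversible before they have had time to resolve.

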ECG parameters will be measured at the specified time points, including heart rate, PR, RR, QRS, QT, and QTcF intervals. Each 12-lead ECG will be performed in triplicate (sequentially within 5 minutes, at least 1 minute apart) and should not be assessed within 1 hour after any major meal or, major meals should be withheld until after ECG assessments. The average of the triplicate ECG readings at the time points collected will be calculated, and changes from baseline values will be assessed. Intensive cardiac assessments will be performed in the Safety Set using food effects on ECG to establish assay sensitivity. Analysis of drug related QT/QTc interval changes relative to serum PK concentrations may be conducted on all dose regimens. The principles of this analysis follow the statistical methods described by Garnett et al. (Garnett, 2018). The ECG utilized for this analysis requires adjudication by qualified cardiologists in accordance with principles set out in the ICH E14 guideline and subsequent Q&A documents. All ECG recordings will be in triplicate and compliant with the correct recording and manual adjudication of ECG in thorough QT/QTc studies. The ECG analyses will be based on adjudicated selected triplicates from each time point.

An outlier analysis will be performed that will summarize the frequency and percentage of participants who meet any of the following outlier criteria at each visit by cohort:

- QT, QTcF interval  $\leq$  450 msec
- $450 \,\mathrm{msec} < \mathrm{QT}$ ,  $\mathrm{QTcF}$  interval  $\leq 480 \,\mathrm{msec}$
- 480 msec < OT, OTcF interval < 500 msec

- QT, QTcF interval > 500 msec
- QT, QTcF interval increases from baseline  $\leq$  30 msec
- 30 msec < QT, QTcF interval increases from baseline  $\le$  60 msec
- QT, QTcF interval increases from baseline > 60 msec

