Woderate (CTCAE Grade 2)			a substantial
QT interval prolongation:	NA	≥ 2	amendment d
A prolongation of the uncorrected QT interval	11/1		
of greater than 500 msec, using consistent,			
technically valid triplicate ECG (CTCAE			
Grade 2)			
Hematology (CTCAE Grade 2):	NA	≥ 2	
Hb drop to absolute values of < 10g/dL (100			
g/L)			
Platelet count drop to absolute values of <			
75,000/mm 			
Severe (CTCAE Grade 3)	NA	2	Study suspended (all
Or			dosing [lower, equal,
Serious AE (not fatal or life-threatening)			or higher doses]
Or			suspended)
Hy's law:			
ALT or AST value $> 3 \times ULN$ together with			Continuation of the
bilirubin increase $> 2 \times ULN$ , without other			cohort or study
evidence of cholestasis (CTCAE Grade 3)			requires a substantial
Or			amendment b
ALT or AST value > 8 × ULN.			
ALT or AST value > 3 × ULN, and			
symptomatic (CTCAE Grade 3) Or			
Injection/infusion site reactions:			
Severe (CTCAE Grade 3)			
Or			
Injection/infusion related reactions (including			
hypersensitivity):			
Severe (CTCAE Grade 3)			
Or			
Hematology (CTCAE Grade 3):			
Hb drop to absolute values of $\leq 8 \text{ g/dL}$			
Serious (fatal or life-threatening, CTCAE	NA	1	
Grades 4 and 5)			

<sup>a For injection/infusion site reactions, a cohort and/or the study will be suspended when ≥ 3 participants are observed. If all but 1 affected participant show signs of recovery (at least to Grade 1), cohort and study continuation can then proceed. If ≥ 2 participants remain at Grade 2 after the minimum data review period, the period of observation should be extended for up to 168 hours. If all but 1 affected participant show sign of

recovery (at least to Grade 1), cohort and study continuation can then proceed. If  $\geq 2$  affected participants remain at Grade 2 after the first 168-hour extension period, the SRC will make the decision to either prolong further the observation period up to a maximum of another 168 hours or suspend the remainder of the cohort and study. At the end of the second extension period, if all but 1 participant show sign of recovery (at least to Grade 1), cohort and study continuation can then proceed. If, however,  $\geq 2$  affected participants remain at Grade 2, cohort and study will be suspended.

b A substantial amendment may include an amendment to the protocol, the ICF, or other study-related documents as appropriate.

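### The QT stopping row in Table 11 uses uncorrected QT alone, so above 60 bpm it can fail to count participants with QTcF above 500 msec, and no other stopping route states a QTcF limit

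*Protocol*

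**What the plan says.** Protocol 10.3.4, Table 11, gives one row to QT prolongation. Its criterion is "A prolongation of the uncorrected QT interval" above 500 msec on technically valid triplicate ECGs. The row is labelled CTCAE Grade 2 and is met at two or more participants. Its action suspends the rest of the cohort and all equal or higher doses. Lower doses may continue, and resuming needs a substantial amendment. The table's first column is headed "Adverse Events Related to Study Intervention", so the events must also be judged related. No row of Table 11 names QTc or QTcF.

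The ECG analysis is wider. Protocol 9.4.1 plans ECG parameters "including heart rate, PR, RR, QRS, QT, and QTcF intervals" and sets a top outlier category of "QT, QTcF interval > 500 msec". SAP 4.13.5 and 6.4 repeat that category.

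Protocol 7.2 has severity graded by clinical judgment and "according to criteria from NCI CTCAE version 5.0", with study-specific modifications that include QT prolongation. It also says: "Unless a cohort stopping rule is met, dose continuation or escalation will proceed as scheduled". The same sentence adds the proviso that no prespecified toxicity event has occurred, as determined by the Safety Review Committee (SRC).

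**The concern.** At a fixed repolarisation time corrected for rate, a faster heart gives a shorter raw QT. A raw limit of 500 msec is therefore a higher bar in QTcF terms at any rate above 60 bpm. Two participants in a cohort could both be in the plan's highest QTcF category without meeting the one row written for QT prolongation.

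Whether dosing stopped would then depend on routes that rest on judgment. This matters most within a cohort. Protocol 4.1 lets further participants be dosed from 48 hours, and the remainder from 72 hours, after the sentinel pair, provided no suspension or stopping criterion has been met. The study is first-in-human, and explicit stopping rows exist for events that nobody expects.

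**Working it through.** The 500 msec limit is a fixed threshold with no derivation in the documents, so there is no plan figure to reproduce. The check is how that limit translates between QT and QTcF.

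**Inputs.** The limit is above 500 msec on uncorrected QT, in at least 2 participants (Table 11). The correction is Fridericia's (Protocol 10.12). Participant heart rates are not in the documents, so a range is shown as an assumption.

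**Formula.** QTcF = QT / (60/HR)^(1/3), and so QT = QTcF × (60/HR)^(1/3).

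| Heart rate (bpm) | QTcF when QT = 500 | QT when QTcF = 500 |
|---|---|---|
| 45 | 454.3 | 550.3 |
| 50 | 470.5 | 531.3 |
| 55 | 485.7 | 514.7 |
| 60 | 500.0 | 500.0 |
| 65 | 513.5 | 486.8 |
| 70 | 526.4 | 475.0 |
| 75 | 538.6 | 464.2 |
| 80 | 550.3 | 454.3 |

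The middle column is the QTcF that must be exceeded before the present row counts anyone. The right column, above 60 bpm, is the QT above which QTcF is already in the top category.

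**Example.** At 75 bpm, (60/75)^(1/3) = 0.9283. QTcF 530 gives QT = 530 × 0.9283 = 492.0 msec. Two such participants are both in the top QTcF category, and the row counts neither.

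**When a given QTcF is missed.** The row does not count QTcF = x once HR ≥ 60 × (x/500)^3. That is 63.7 bpm for 510, 67.5 for 520, 71.5 for 530, 75.6 for 540 and 79.9 for 550.

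**Effect of counting either measure.** Above 60 bpm the newly counted QT values are about 487 to 500 msec at 65 bpm, 475 to 500 at 70, 464 to 500 at 75 and 454 to 500 at 80. Below 60 bpm QTcF is lower than QT, so the result is the same as now: QT 525 at 50 bpm (QTcF 494.0) and QT 545 at 45 bpm (QTcF 495.2) still count. A criterion met by either measure cannot drop anyone whom the QT limb counts today. Substituting QTcF for QT would drop some: QT 500 to 514.7 at 55 bpm, 500 to 531.3 at 50 and 500 to 550.3 at 45.

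**The other routes.**
- Generic Grade 2 row: if reversible, at least 3 in one System Organ Class (SOC) or at least 4 across SOCs; if not, at least 2 in different SOCs. Two QT cases alone, coded to one SOC, meet none of these.
- Grade 3 and non-fatal serious-event criteria: 2 participants, all dosing suspended. Entry depends on how the Investigator grades or classifies the event.
- Acute-event stop and prespecified-toxicity proviso (7.2): neither gives a QTcF value.
- SRC review (4.3): 14-day data including ECG findings after Cohorts 1, 2 and 5. Table 8 lists no escalation review after Cohort 6.
- Investigator's veto (6.6): "Alexion may not supersede the Investigator if there are concerns that dosing should be stopped". No limit is stated.

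**The case against.** The strongest objection is that the row is only one of several safeguards. A clinically significant ECG abnormality is itself an adverse event under Protocol 10.3.1. It can therefore enter the generic Grade 2 row, the Grade 3 row or the serious-event criterion, and the SRC sees the ECG findings. This stands, and it limits the point to one row. A reader might infer that the study has no way to stop for QTcF above 500 msec. The documents do not support that. Nor can they settle whether the Grade 3 row already covers it, because the CTCAE v5.0 text is not in them. What remains is that no route states a QTcF limit.

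A second objection is that the outlier categories in 9.4.1 are descriptive bins on adjudicated ECGs and need not be dosing triggers. That is right. A reader might infer that the analysis and the stopping rule contradict each other, but they serve different purposes. The categories show only that the plan already treats 500 msec as a notable level for both measures. Section 7.2 shows that the QT entry was tailored to this study, so this is a design choice that could be improved.

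A third objection concerns the remedy. Putting QTcF into a row labelled Grade 2, with partial suspension, could weaken the response if the same event would otherwise be graded 3 and suspend all dosing. Tying the row to the triplicate mean would also alter the QT limb: readings of 506, 504 and 485 average 498.3 (1495/3), so a mean rule would miss a case that the present wording leaves open. Both points are sound, and the fix is worded to meet them.

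Finally, likelihood. ECGs are taken after supine rest, participants with clinically significant abnormal ECGs are excluded at Screening or predose (5.2), and Table 4 lists no cardiac risk. This bears on how often the gap would matter, not on whether it exists.

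**Conclusion.** The point holds in a limited form. Above 60 bpm the QT row of Table 11 can fail to count participants with QTcF above 500 msec. The shortfall is about 14 msec of QTcF at 65 bpm, 26 at 70, 39 at 75 and 50 at 80. No other stopping route in the documents states a QTcF limit.

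The figures rest on Fridericia's formula and an assumed range of heart rates. Frequency cannot be estimated, since it would need the participants' heart rates and any drug effect on QT. A reader might infer that a missed stop is likely, or that QTcF should replace QT. The documents support neither: nothing in them points to an expected QT effect, and replacement would lose stops below 60 bpm. This is a cheap improvement to a safeguard.

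**What to change.** Keep the existing wording of the Table 11 QT row and add QTcF as an alternative: after "A prolongation of the uncorrected QT interval", insert *or of QTcF*. Leave the 500 msec limit, the triplicate-quality requirement, the count of at least 2 participants and the action unchanged. Do not insert a reference to the triplicate mean.

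Add one sentence stating that this row is a minimum trigger, and that it neither lowers the grade of nor displaces any event that also meets the Grade 3, serious-event or Grade 4/5 rows. With that sentence no existing stop is lost.

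The cost is one table row, by substantial amendment with ethics and health authority approval before implementation (10.1.1). The trigger becomes somewhat more sensitive above 60 bpm. A stop under it would suspend equal or higher doses and need a further amendment to resume. The requirement for two participants with related events limits that risk. No new assessments are needed, because heart rate, QT and QTcF are already planned at the ECG time points.
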